and tolerability of PZQ in monotherapy. Adult participants with asymptomatic *Plasmodium falciparum* infection will be randomly allocated to one of two study arms with 22 participants in a placebo arm and 22 in an intervention arm with PZQ 40mg/kg once-daily dosing for 3 days.

Study overview

Trial Design

Single-center, assessor-blinded, randomized, placebo-controlled trial

Population

Adult, male or female, aged ≥ 18 years with asymptomatic *Plasmodium falciparum* infection between 200-5000 parasites/ μ l

Intervention

Oral treatment with PZQ 40mg/kg/day administered as once-daily dose for 3 consecutive days.

Control

Placebo administered as once-daily dose for 3 consecutive days.

Outcome

Parasitemia undetectable by thick blood smear on D7 after the start of administration of study drugs

Aims

To assess efficacy of PZQ in asymptomatic participants with *Plasmodium falciparum* parasites

Objectives

Primary Objective:

- To assess the proportion of participants with microscopically-determined parasite clearance on D7 after administration of PZQ compared with placebo

Secondary Objectives:

- 1) To assess the proportion of participants with $\geq 90\%$ parasitemia reduction on D7 compared with baseline between PZQ and placebo study arms
- 2) To assess the time to microscopically-determined parasite clearance in the PZQ study arm compared with the placebo arm
- 3) To assess the safety and tolerability of PZQ 40mg/kg once-daily dosing for 3 days
- 4) To assess the time to qPCR-determined parasite clearance in the PZQ study arm compared with the placebo arm
- 5) To assess the qPCR-determined cure rate in the PZQ study arm compared with placebo at D7 after study drug administration
- 6) To assess and compare the baseline-adjusted parasite mass of participants in the PZQ study arm compared with participants in the placebo study arm

Exploratory Objectives:

To assess activity of PZQ on gametocyte carriage

Rationale for trial design and praziquantel

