To calculate the sample size, we estimated that only 10% of participants in the placebo group will have a parasitemia below the microscopic limit of detection on day 7 versus 50% in the intervention group. With a power of 80% and an alpha error of 5% and considering a ratio 1:1 (treatment versus placebo group), we need 20 subjects in the placebo group and 20 subjects in intervention group. Accounting for a possible dropout rate of 10% in each study arm the final sample size will require recruitment of a total of 44 subjects.

Endpoints and assessment methods

Primary endpoint:

Parasitemia undetectable by thick blood smear on D7 after the start of administration of study drugs

Assessment method: Light microscopy

All those needing rescue treatment according to the physicians' judgement before day 7 will be counted as treatment failures together with all positives at day 7.

Secondary endpoints:

1) Parasitemia reduction $\geq 90\%$ on D7 compared with baseline assessed by light microscopy of thick blood smears

Assessment method: Light microscopy

2a) Time to parasitemia level < 100 parasites/ μl in the PZQ 3-day treatment group versus placebo assessed by microscopy

Assessment method: Light microscopy

2b) Time to parasitemia level below microscopic limit of detection in the PZQ 3-day treatment group versus placebo assessed by microscopy

Assessment method: Light microscopy

3) Occurrence of adverse events (AEs) in the PZQ 3-day treatment group versus placebo

Assessment method: Clinical examination and laboratory analysis

4) Time to parasite clearance assessed by qPCR in the PZQ 3-day treatment group versus placebo

Assessment method: Quantitative PCR

5) Parasitological cure rate assessed by qPCR on D7 after administration of study drugs

Assessment method: Quantitative PCR

6) Area under the curve (AUC) of microscopically-determined parasite mass between D0 and D7 in the PZQ 3-day treatment group versus placebo

Assessment method: Light microscopy

Exploratory endpoints

Proportion of participants with detectable gametocytes during D3-D7 in the treatment group versus placebo

Assessment method: Light microscopy

Duration of the study

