Participants fulfilling all inclusion/exclusion criteria will be randomly allocated to receive either placebo once-daily dosing for 3 days, or PZQ 40mg/kg once-daily dosing for 3 days. The allocation ratio is 1:1. Randomization lists will be created using permuted blocks. Treatment allocation codes will be stored in opaque-sealed envelopes on whose surface is a pre-defined allocation sequence number. Each time a participant fulfils the inclusion criteria the opaque-sealed envelope with the next allocation sequence number is opened by the pharmacist or his delegate. During the treatment period all participants will be hospitalized for three days. Study procedures during the treatment period and follow-up visit will be the same in the two study arms.

Study procedures

Blinding

Laboratory investigators processing and analysing biological samples will be blinded to group allocation. The unblinded pharmacist or designate will prepare the treatment assigned by the randomization system and complete the corresponding treatment record form. Subsequently, verum and placebo will be administered by a physician who is not involved in diagnostic and analytic processes of the study. Other study physicians and study participants will be unaware of group allocation. Only the pharmacists and the physician administering verum and placebo know the group allocation. Verum and placebo are similar but not identical and will be administered to each participant separately out of the original packaging without changing labels.

Procedures will be performed at the time points indicated in the schedule of procedures (Table 2). Additional procedures or laboratory tests may be performed at any time, at the discretion of the investigators if clinically necessary.

Ascertainment of basic demographic information, clinical and past medical history

- Full medical history
- Prior concomitant medication
- Demographic data (gender, age)
- Clinical examination (including measurement of height and weight)
- Vital signs (including pulse, blood pressure and body temperature)

Blood sampling and laboratory tests

A series of blood samples will be drawn to perform different tests. Types of tests to be performed include molecular biology, biochemistry, haematology and parasitology.

Details of these tests are as follows:

Parasitology:

These tests include thick and thin blood smears and qPCR to detect the malaria parasite.

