- **Thick and thin blood smears** are prepared at screening. During the treatment period (D0, D1 and D2) thick and thin blood smears are prepared 6-hourly. Between D3 and D7 thick and thin blood smears will be prepared once daily. While thick blood smears will be used for quantification of parasitemia, thin blood smears will be used for determination of *Plasmodium* species.
- **Blood in RNA later (for qPCR)** is sampled at the same time as thick and thin blood smears. It is sampled at screening and during the treatment period (D0, D1 and D2) blood in RNA later it is sampled 6-hourly. Between D3 and D7 blood in RNA later will be sampled once daily.

Hematology, biochemistry tests:

These tests include full blood count, aspartate aminotransferase (AST), alanine aminotransferase (ALT), alkaline phosphatase, gamma-glutamyl transferase (GGT), total bilirubin, conjugated bilirubin, albumin, lactate dehydrogenase (LDH), creatinine, urea, glucose, sodium, potassium, calcium, and magnesium. These tests will be performed at screening, D3 and D7.

Urine sampling

- **Urine β -HCG test in female participants:** This is performed at screening to rule out any potential pregnancy at the beginning of the trial.

Administration of praziquantel

Participants allocated to the PZQ intervention group will receive PZQ orally on D0 once that the presence of all inclusion criteria and the absence of all exclusion criteria are secured. The dose will be 40 mg/kg once-daily for 3 days. Also, placebo will be administered orally, once daily for 3 days. To increase PZQ plasma levels study drugs will be administered with a standardised meal (40,42,43). Co-administration with food will also help to mask the taste of PZQ, thereby making it more similar to placebo and reducing the chance of reporting bias.

Clinical visits

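### Participant blinding is stated but not secured, because non-identical drug and placebo come from original packs with labels unchanged; the main exposure is self-reported adverse events

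*Protocol*

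**What the plan says.** The protocol labels the design "Single-center, assessor-blinded, randomized, placebo-controlled trial" (Synopsis and Trial Design). The Blinding paragraph under Study procedures then goes further than that label:

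- Laboratory: "Laboratory investigators processing and analysing biological samples will be blinded to group allocation".
- Clinic and participants: "Other study physicians and study participants will be unaware of group allocation".
- Dosing: the product is prepared by an unblinded pharmacist and "administered by a physician who is not involved in diagnostic and analytic processes of the study".
- Product: "Verum and placebo are similar but not identical and will be administered to each participant separately out of the original packaging without changing labels".

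Under Administration of praziquantel, study drug is given with a meal, partly to mask the taste of praziquantel, "thereby making it more similar to placebo and reducing the chance of reporting bias".

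Two endpoints bear on this. Secondary endpoint 3 compares adverse events between the arms. The primary endpoint carries the rule "All those needing rescue treatment according to the physicians' judgement before day 7 will be counted as treatment failures", along with everyone who is smear-positive on day 7. The section on treatment of the infection lists the investigator's own judgement as a separate trigger for rescue.

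**The concern.** One paragraph makes a promise about what participants know and then fixes a dosing procedure that works against it. The label is a more direct cue than taste, yet taste is the only cue that the protocol deals with.

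Participants' knowledge matters most for adverse events. Table 2 has them ascertained at 17 scheduled visits (12 from H0 to H66 and 5 from D3 to D7). The severity scale rests largely on awareness, discomfort and tolerance, and several of the commonest listed praziquantel effects, such as nausea, headache, drowsiness and abdominal pain, are known mainly from what the participant says. A participant who knows the arm may report more on drug or less on placebo. Causality, assigned by the site principal investigator, draws on the same histories.

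A second route runs to the primary endpoint, since a rescue decision based on judgement can follow reported symptoms. The dosing physician, who knows the allocation, is kept out of diagnosis and analysis, but the text does not say whether this covers adverse event assessment or the decision to rescue.

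**Working it through.** **1. Is anything concealed from the participant?** The stated protections, set against what each one covers:

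| Protection in the protocol | What it covers | Hides the participant's own label? |
|---|---|---|
| Unblinded pharmacist prepares treatment | Keeps other staff blind | Not stated |
| Separate dosing physician | Keeps other physicians blind | No |
| Each participant dosed separately | Stops one participant seeing another's product | No |
| Given with food | Taste | No |
| Blinded laboratory staff | Smear, qPCR, haematology, biochemistry | No |

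No over-labelling, repackaging or opaque container is described, and the one sentence on packaging says that labels are left as they are.

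**2. The plan's own sample size.** Inputs from Sample size: 10% versus 50%, power 80%, alpha 5%, ratio 1:1. Two-sided, pooled variance, no continuity correction:

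n = [1.960·√(2·0.30·0.70) + 0.8416·√(0.10·0.90 + 0.50·0.50)]² / 0.40² = (1.270 + 0.491)² / 0.16 = 19.4, so 20 per arm.

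This reproduces the stated 20 per arm. With the 10% allowance, 40 × 1.1 = 44, or 22 per arm. These figures do not depend on the blinding point.

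**3. Scale for adverse events.** The section on potential risks gives six effects at 10% or more (nausea, vomiting, abdominal pain, headache, drowsiness, urticaria). This is a floor, so a range is shown. Two prompted reports are an illustration, not an estimate; they add 2/22 = 9.1 points.

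- True rate 10%: 0.10 × 22 = 2.2 cases; (2.2 + 2)/22 = 19.1%.
- True rate 20%: 0.20 × 22 = 4.4 cases; (4.4 + 2)/22 = 29.1%.

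The near-doubling therefore holds only at the floor.

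**4. Scale for the primary endpoint.** A day-7 positive is already a failure, so rescuing that participant changes nothing. Only rescue of someone who would have been smear-negative on day 7 counts. On placebo at the planned 10%, that is 0.10 × 22 = 2.2 people; the other 19.8 cannot be altered.

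**5. Effect on the primary test.** The documents give no rescue rate, so the shares below are assumptions. Assume no drug effect, 20 evaluable per arm and a Pearson chi-square test at 5%. The rejection rate, by exact binomial enumeration, when a share of would-be placebo clearers is rescued because of knowledge of the arm:

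| True clearance, both arms | 0% rescued | 30% rescued | 50% rescued |
|---|---|---|---|
| 10% (planned placebo rate) | 3.9% | 4.2% | 5.4% |
| 30% | 5.3% | 10.1% | 20.5% |
| 50% | 4.3% | 15.0% | 37.5% |

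At the planning value the error rate hardly moves. It grows only if clearance without a drug effect is well above plan and a large share of those clearers is also rescued.

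**The case against.** The best defence is that the trial is called assessor-blinded, never double-blind, and that the assessment which matters most, the day-7 smear, is read by blinded staff. That stands for the parasitology and also for the laboratory safety values. It does not answer the point, because the Blinding paragraph itself extends blinding to participants, and adverse events are also found by clinical contact.

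A second defence is that the packaging sentence says where the product comes from and not that the pack is shown. A pharmacist prepares the treatment and a dedicated physician gives it, so exposure is not established. This also stands: concealment is unsecured, but the text does not prove that unblinding occurs. Likewise, a participant who sees only one product cannot compare the two, so a difference in appearance alone need not reveal the arm. The unaltered label is the real cue.

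The protocol also refers to a separate SOP on unblinding. It concerns breaking the code for medical reasons, not hiding the product.

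Three stronger readings are tempting, and the documents do not support them:

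- A reader might infer that participants share a ward and compare products. The protocol says only that they are hospitalised.
- A reader might infer that every influenced rescue decision moves an arm by 1/22 = 4.5 points. Most rescues on placebo would move it by nothing, because day-7 positives are failures already.
- A reader might infer that rescue decisions are made with knowledge of the arm. Physicians other than the dosing one are said to be blinded, and two of the three rescue triggers require parasitaemia with fever or with severe disease. Leakage would have to come through participants or through the loosely defined role of the dosing physician.

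**Conclusion.** The point holds in a limited form. The protocol claims that participants are blinded and, in the same paragraph, fixes a dosing procedure that leaves the claim unsecured.

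The main exposure is the between-arm comparison of self-reported adverse events. With 22 per arm, a few prompted reports are visible against expected counts that start at about 2 per effect. Whether such reports would occur, and how many, cannot be derived from the protocol.

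The primary endpoint is exposed only through early rescue based on judgement. At the planned 10% placebo clearance about 2 of 22 could be affected, and the false-positive rate rises from 3.9% to 5.4% even if half of the would-be placebo clearers are rescued. The larger figures above rest on clearance rates and rescue shares that are assumed. The main efficacy inference, based on blinded smears, is not undermined.

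**What to change.** 1. In the Blinding paragraph, replace the clause on original packaging and unchanged labels with an instruction that the pharmacist, who is already unblinded, removes the product from its pack and dispenses it in a plain opaque container bearing only the allocation number.
2. State that the dosing physician's exclusion from diagnosis and analysis also covers adverse event assessment and rescue decisions. This concerns who decides; the rescue criteria themselves are not touched.
3. If concealment is not feasible, withdraw the statement that participants are blinded and report the adverse event comparison as not participant-blinded.

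The cost is a little more pharmacy time and an added drug-accountability step. One limit remains: the tablets are still similar but not identical, so the container removes the label as a cue but not every difference in appearance. The change has to be in place before dosing, because a participant who has seen the label cannot be re-blinded. For anyone already dosed under the present text, item 3 applies.

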Participants will be hospitalized for at least 3 days or up to 7 days, depending on the participant convenience. After discharge, subjects will return daily to the Clinical Center for further assessments until Day 7. The duration of involvement in the study from day 0 (day of administration of first PZQ dose) will be 7 days. The start of the trial is defined as the date of the first visit (i.e. screening visit) of the first participant. The end of the trial is the date of the last visit of the last participant.

Potential risks for participants

Phlebotomy

The maximum volume of blood drawn over the study period is approximately 61 ml over 7 days. Additional blood samples could be required for safety reasons. However, this volume should not compromise these otherwise healthy participants. There may be minor bruising, local tenderness or presyncopal symptoms associated with venepuncture, which will not be documented as AEs if they occur. Rare side effects are infections, thrombophlebitis and neural lesions. In the case a participant develops severe discomfort from repeated venepunctures, and only with the recommendation/concurrence of the clinical team, an intravenous catheter could be inserted in one of the upper limbs of the participant to take the remaining blood samples as per protocol. An additional 2 mL of blood will be taken with each blood drawn when using the intravenous catheter. The participant will be informed about this extra volume of blood to be drawn before the catheter insertion.

Praziquantel

Side effects of praziquantel include nausea ($\geq 10\%$), vomiting ($\geq 10\%$), gastrointestinal and abdominal pain ($\geq 10\%$), headache ($\geq 10\%$), drowsiness ($\geq 10\%$), urticaria ($\geq 10\%$), diarrhoea

(<10%), anorexia (<10%), dizziness (<10%), somnolence (<10%), fever (<10%), rash (<10%), myalgia (<10%), unspecific arrhythmia (<0.0001%), pruritus (<0.0001%), seizure (<0.0001%), allergic reaction (<0.0001%), eosinophilia (<0.0001%) (41).

Potential benefits for participants

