The procedures to be included in each visit are documented in Table 2. In General, during the treatment period (D0-D2) each visit is assigned a time point and a window period of ± 2 hours within which the visit will be conducted. Only the visits with study drug dosing time points (i.e. H0, H24, H48) are exempted from this and have a stricter window period of ± 1 hour. Between D3 and D7 the visit can be performed at any given timepoint on the respective day considering participant and study team convenience. Patients must be seen for all visits on the designated day within the given window period, or as close to it as possible. Missed or rescheduled visits should not lead to automatic discontinuation.

Screening visit

All potential participants will have a screening visit, which shall take place on the same day (i.e. within 24 hours) as the administration of study drugs. Informed consent will be obtained from those eligible as described above. Once the informed consent is signed, the following screening procedures indicated in Table 2 will be undertaken:

- Full medical history, clinical examination (including measurement of height and weight) and ascertainment of demographic details
- Vital signs (pulse, blood pressure and temperature);
- urine β -HCG test in female participants;
- Blood samples will be taken for full blood count, biochemistry, thick and thin blood smears, blood for RNA later.
- The inclusion and exclusion criteria for the study will be assessed

AEs will be recorded from the signature of the informed consent onwards. Abnormal clinical findings from the medical history, vital signs assessment or blood tests at any point in the study will be assessed using established reference intervals of CERMEL laboratory. If a laboratory test is out of range it may be repeated to ensure it is not a single occurrence. If an abnormal finding is deemed to be clinically significant, the participant will be informed and appropriate medical care arranged with the permission of the participant.

Study drug administration (D0-D2; H0, H24 and H48)

Medication will take place at CERMEL and participants will be hospitalized for 3 days. Before the medication is administered the following measures will be performed on all participant:

- Vital signs
- Thick and thin blood smears
- Blood in RNA later
- Potential adverse events (AEs)
- Potential concomitant medication is ascertained

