Urine β-HCG	x									x									(x)
'Adverse events' and 'concomitant medication'		x	x	x	x	x	x	x	x	x	x	x	x	x	x	x	x	x	x
Study drug administration		x				x				x									
Malaria rescue treatment																			(x)
Full blood count (1.2ml)	x													x				x	(x)
Biochemistry** (2.7ml)	x													x				x	(x)
Thick and thin blood smears (0.2ml)	x	x	x	x	x	x	x	x	x	x	x	x	x	x	x	x	x	x	x
Blood in RNA later (0.5ml)	x	x	x	x	x	x	x	x	x	x	x	x	x	x	x	x	x	x	x
Blood volume (total = 24.3 ml)	4.6 ml	0.7 ml	0.7 ml	0.7 ml	0.7 ml	0.7 ml	0.7 ml	0.7 ml	0.7 ml	0.7 ml	0.7 ml	0.7 ml	0.7 ml	4.6 ml	0.7 ml	0.7 ml	0.7 ml	4.6 ml	

(x) = if judged necessary by clinical investigator; Note that additional assessments at other time points may be performed if judged medically necessary by the clinical investigator

* Including pulse, blood pressure, temperature;

** Biochemistry: Aspartate aminotransferase (AST), alanine aminotransferase (ALT), alkaline phosphatase, gamma-glutamyltransferase (GGT), total bilirubin, conjugate bilirubin, albumin, lactate dehydrogenase (LDH), creatinine, urea, glucose, sodium, potassium, calcium, and magnesium

Assessment of safety

Safety of PZQ treatment will be assessed by analysing the frequency, incidence and nature of adverse events and serious adverse events arising during the study.

Definitions

Adverse Event (AE)

An Adverse Event (AE) is any new unfavourable and unintended sign, symptom, or disease temporally associated with the use of a medical treatment or procedure that may or may not be considered related to the medical treatment or procedure. An AE is a term that is a unique representation of a specific event used for medical documentation and scientific analyses. Each AE has to be documented in order of appearance, given by a number. In addition, the start and end time of the AE has to be noted precisely. The investigator must enter the information within 24 hours in the paper-based source document and eCRF using the AE section.

The term 'new' unfavourable and unintended sign/symptom/disease implies that this 'new' sign/symptom/disease was not present at baseline or was not part of the past medical history of the participant.

Example: In case a patient reports sleeping problems at baseline and further reports 'sleeping problems' during follow up, then 'sleeping problems' will not be counted as adverse events.

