Exceptions from this rule can be made if the problem, if a clinician is convinced the respective sign/symptom/disease has become much different in severity/intensity, quality etc.

Grading of adverse events

The investigator will assess the **severity/intensity** of the adverse event using the following terms:

Table 3: Severity of Adverse Events

Grade 1	Mild	Awareness of sign or symptom, but easily tolerated; Transient or mild discomfort (< 48 hours); no medical intervention/therapy required
Grade 2	Moderate	Enough discomfort to cause interference with usual activity; Mild to moderate limitation in activity* - some assistance may be needed; no or minimal medical intervention/therapy required
Grade 3	Severe	Incapacitating with inability to work or do usual activity; Marked limitation in activity**, some assistance usually required; medical intervention/therapy required, hospitalisations possible
Grade 4	Life-threatening	Note: this must also be reported as Serious Adverse Event; Extreme limitation in activity, significant assistance required; significant medical intervention/therapy required, hospitalisation or hospice care probable
Grade 5	Death	Note: this must also be reported as Serious Adverse Event

*Includes limitation in instrumental activities of life: preparing meals, shopping for groceries or clothes etc

**Includes limitation in self-care activities of life: bathing/showering, dressing/undressing, feeding self, using the toilet etc

Serious or Life-Threatening AEs

ANY clinical event deemed by the clinician to be serious or life-threatening should be considered a grade 4 event. Clinical events considered to be serious or life-threatening include, but are not limited to: seizures, coma, tetany, diabetic ketoacidosis, disseminated intravascular coagulation, diffuse petechiae, paralysis, acute psychosis, severe depression.

Causality assessment between study medication and AE

Afterwards the investigator has to decide a term for describing the relationship to the study drug:

Table 4: Relationship to Study Drug (Causality assessment)

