A decision on medical and scientific grounds is required to assess whether an immediate notification of an event is warranted in other situations, such as medically important events which are not life-threatening, fatal or cause hospitalization, but could endanger the patient or required an intervention to prevent one of the above conditions developing.

Remark: Examples of such events are intensive care in the emergency room or at home to treat a bronchospasm; convulsions not causing hospitalisation, or the development of drug addiction or drug abuse.

Monitoring of AEs (including SAEs)

The Site Principal Investigator (PI) will make a causality assessment. He should be informed about any new data on a participant for whom a causality link had already been established to reconsider its analysis and if necessary reassess the causality. Data shall only be modified following an official query procedure. Source Document review meetings shall be organised regularly, during which the site PI and the local study team shall review AE data (intensity, causality, and date of event manifestation in relation to the start of treatment). Safety data should be entered immediately in the eCRF.

A Medical Monitor will be available for the trial site to resolve arising safety related questions and uncertainties. He will oversee the medical aspects of the clinical trial and will actively collaborate with the sites. The medical monitor will have access to the eCRF and can address a request to the site PI concerned to add any further information needed for the safety analysis. The medical monitor will conduct the final review of the eCRF for any participants who have had an adverse event.

Obligation of AE and SAE notification

Adverse Events

The AEs, regardless of their seriousness and causal relationship to the study drug, arising between the first administration of study medication and the last study visit (as per the protocol), must all be recorded on the participant's Source Document (AE recording section). When possible, the symptoms must be regrouped within a single syndrome or diagnosis. The healthcare personnel shall have to specify the date of manifestation of the event, its intensity, final evolution, the measures taken and the treatment undertaken (if any).

Serious Adverse Events (SAEs)

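### The adverse-event definition does not capture ordinary worsening of a baseline symptom, and its past-history clause is ambiguous, so secondary endpoint 3 is undercounted

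*Protocol*

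**What the plan says.** Under Assessment of safety, Definitions, the protocol states: "An Adverse Event (AE) is any new unfavourable and unintended sign, symptom, or disease temporally associated with the use of a medical treatment or procedure". It then explains that a new sign, symptom or disease is one that "was not present at baseline or was not part of the past medical history of the participant". The worked example is a patient who reports sleeping problems at baseline and again during follow-up; it ends "then 'sleeping problems' will not be counted as adverse events". Exceptions are permitted, not required, and apply "if a clinician is convinced the respective sign/symptom/disease has become much different in severity/intensity, quality etc".

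Secondary endpoint 3 uses this definition: "Occurrence of adverse events (AEs) in the PZQ 3-day treatment group versus placebo". The section on the risks of praziquantel ("Side effects of praziquantel include nausea" and so on) lists nausea, vomiting, abdominal pain, headache, drowsiness and urticaria, each at 10% or more.

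The start of AE recording is given twice. The Screening visit section says "AEs will be recorded from the signature of the informed consent onwards". The section on the obligation of AE and SAE notification covers events "arising between the first administration of study medication and the last study visit".

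**The concern.** This is a rule about what enters the AE section of the case report form. An event that fails the definition is never recorded as an AE, so no later analysis can recover it.

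The rule bears on the complaints that praziquantel is known to cause. Nausea, headache and drowsiness are ordinary symptoms that an adult may well have at screening or mention in a medical history, and the protocol sets no limit on how far back that history goes. If the drug makes such a symptom return or worsen, the extra events arise mainly in the praziquantel arm, so discarding them narrows the apparent gap from placebo. For a trial that presents safety and tolerability of a three-day course as an objective, that error flatters the drug.

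**Working it through.** No figure in the protocol depends on this definition, so the check is mainly one of reading.

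**Two readings of the clause.** The limbs are absence at baseline and absence from the past history, joined by *or*. Read literally, either absence makes a symptom new. Read strictly, both are needed.

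| At baseline | In history | Literal reading | Strict reading |
|---|---|---|---|
| no | no | new | new |
| no | yes | new | not new |
| yes | no | new | not new |
| yes | yes | not new | not new |

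**What the example settles.** The example excludes a symptom reported at baseline. That fits the strict reading. It also fits the literal one, because the full medical history is taken at the same screening visit, so a complaint reported there is both present and in the history. The example therefore does not decide the second row: a past headache, absent before dosing, that returns after dosing. Two investigators could classify it differently, and each could cite the text.

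**What holds on both readings.** A symptom present at baseline and in the history is not new. If it worsens on treatment, only the exception can make it an AE. The exception is optional, depends on one clinician's conviction and asks for a large change. Table 3 defines five severity grades, so a move from grade 1 to grade 2 can be measured, but nothing says that such a move meets the threshold.

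**Comparison with the rest of the protocol.** The AE definition itself admits events whether or not they are related, and the notification section requires AEs to be recorded whatever their cause. Table 4 already weighs the participant's known clinical condition when causality is judged. The definition uses history one step earlier, before causality is considered. Annex 1 grades ALT, AST, alkaline phosphatase and bilirubin against an abnormal baseline, so the protocol recognises worsening from baseline for these laboratory values; symptoms have no equivalent rule.

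**Illustration of size.** Let p be the true proportion with onset, recurrence or worsening of a given symptom after the first dose, and h the share of those events that the rule discards. The expected recorded count among the 22 praziquantel participants is 22 × p × (1 − h). The value p = 10% is the floor listed for the common reactions; p = 30% and all values of h are assumptions.

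| p | h = 0 | h = 10% | h = 25% | h = 50% |
|---|---|---|---|---|
| 10% | 2.2 | 1.98 | 1.65 | 1.10 |
| 30% | 6.6 | 5.94 | 4.95 | 3.3 |

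At p = 10%, the chance of recording at least one case is 1 − (1 − p(1 − h))^22, which gives 90.2%, 87.4%, 82.0% and 67.6% across the four columns.

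If h is the same in both arms, the recorded difference is (1 − h) × (p on praziquantel − p on placebo). The absolute difference shrinks by the factor 1 − h; the ratio of the two rates does not change. On the literal reading h is smaller, because fewer events are discarded.

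**Start of recording.** Consent and first administration are different start points. Screening takes place within 24 hours of dosing, so the disputed interval is at most that long. Table 2 does not resolve it: it has no AE mark at screening, and its first check is at H0, which the study drug administration section places before the dose.

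**The case against.** The strongest reply is that the text, taken literally, already counts a resolved past symptom that returns after dosing, and that the protocol gives no example of one being discarded. This stands. A reader might infer that anything ever mentioned in the history is barred from being an AE; the documents do not establish that, only that the wording allows it.

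It can also be said that worsening has an outlet, and that these participants are asymptomatic with significant disease excluded. The outlet exists but is optional and set high. Asymptomatic is defined by absence of fever, so it does not rule out headache or abdominal discomfort at baseline.

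A reader might infer that serious events are lost too, for instance a seizure in someone with earlier seizures. The section on serious or life-threatening AEs counts any clinical event judged serious as grade 4, names seizures, and does not repeat the newness condition; Table 3 then requires SAE reporting. The SAE definition does begin from an adverse event, so the wording is not perfectly joined up, but it does not support a claim that such events go unreported.

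Finally, a loss of power might be claimed. The Statistics section plans descriptive summaries for secondary endpoints and the protocol states no power for AEs, so a power figure would rest wholly on invented rates.

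**Conclusion.** The point holds in a limited form. Ordinary worsening of a symptom already present at baseline is not captured unless a clinician invokes the exception. Recurrence of a symptom found only in the history may or may not be captured, depending on how the clause is read. Secondary endpoint 3 is therefore undercounted, and if praziquantel causes more of these events than placebo, the absolute difference is biased towards zero.

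The documents do not show that the common reactions drop out of the endpoint. The loss is symptom by symptom and touches only participants with that symptom at baseline or, on the strict reading, in the history; a participant with past headaches who develops nausea can still have an AE. The size cannot be derived, because the documents give neither baseline nor history prevalence. The counts above only show how it scales, and the unchanged ratio assumes equal discarding in both arms.

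The contradiction on when AE recording starts is real but separate. It covers a short interval and does not add to the undercount after dosing.

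**What to change.** Define an AE for the endpoint as any unfavourable sign, symptom, disease or laboratory change that begins, recurs, or worsens by at least one grade relative to its status just before the first dose, counted from that dose to D7. For haematology and biochemistry the screening sample serves as the reference, since Table 2 schedules none at H0. Delete the past-history clause and the threshold of marked change, and use history only in the causality assessment in Table 4. Replace the sleeping-problem example with one that shows an unchanged symptom (not an AE) and a one-grade worsening (an AE).

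Reconcile the Screening visit section with the notification section: record from consent, and list events before the first dose separately as pre-treatment.

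The cost is a wording change in the protocol and the case report form instructions, slightly more AEs to enter, and a somewhat less favourable AE count. The change must be in place before the events are recorded, because it cannot be applied at analysis.
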